4.2 Analysis methods

4.2.1 Demography

The following will be reported on subjects who are randomised: sex, age, race and ethnic group, baseline Hb value, geographical region, incident vs stable dialysis (dialysis duration ≤ 4 months vs > 4 months from the randomization date), dialysis type, cardiovascular/cerebrovascular/thromboembolic medical history, congestive heart failure history, coronary artery disease history and cerebrovascular history, other relevant medical and surgical history, concomitant medication, weight, height, BMI, tobacco use, CKD diagnosis, diabetes history and baseline blood pressure. Continuous and categorical demographic variables will be presented as described in Section 4.1. The following continuous variables will also be presented as range-based categories:

- baseline Hb value (≤ 10.5 g/dL vs > 10.5 g/dL),
- age ($\geq 18 - < 50$, $\geq 50 - < 65$, $\geq 65 - < 75$, ≥ 75 years),
- BMI (< 30 , ≥ 30 kg/m²), and
- weight (< 70 , $\geq 70 - < 100$, ≥ 100 kg).

4.2.2 Confirmatory analysis for the efficacy endpoints

To address the issue of multiple testing while maintaining the overall type-I error, adopting a 5% two-sided significance level, a closed testing sequence will be used for the efficacy endpoints. First, the primary efficacy endpoint analysis according to Section 0 will be performed. If successful, the testing will continue with the secondary efficacy endpoints in the order as specified in Section 4.3.4. Confirmatory statistical hypothesis testing will continue until the first statistically non-significant treatment difference is observed. However, treatment comparisons following and including the first non-significant comparison will be examined in an exploratory manner.

All analyses other than part of this confirmatory analysis will be interpreted descriptively. Consequently, no adjustments for multiplicity will be necessary for such analyses. Ninety-five percent confidence intervals will be calculated, where appropriate, as measures of study precision. P-values may be calculated but are to be regarded as descriptive.

4.2.3 Time to event analysis

For time to event variables, treatments will be compared using a Cox proportional hazards model. Unless specified otherwise baseline Hb as a continuous variable will be used as a covariate, and treatment group, CV history, dialysis duration and geographic region as fixed effects for all analyses. The Efron method will be used for ties. The p-values (calculated using the Wald test), hazard ratio (HR) and 95% confidence intervals for the HR will be reported. Summary tables of these analyses will also include the number of subjects with an event and Kaplan-Meier estimates of the event rates per treatment group estimated at a time point determined on the basis of the available follow-up. Kaplan-Meier estimates of the cumulative proportion of subjects with events will be estimated and plotted, with the number of subjects at risk indicated below the plot at specific time points.

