1.2 Study design

This is a Phase 3, multicenter, randomized, open-label, active-controlled study to evaluate the safety and efficacy of roxadustat compared to epoetin alfa for the treatment of anemia in dialysis subjects. Subjects on hemodialysis (HD) or peritoneal dialysis (PD) who have been treated with an erythropoietin analogue or have an indication for treatment with an erythropoietin analogue will be evaluated for eligibility and randomized at a 1:1 ratio to treatment with roxadustat (with discontinuation of prior erythropoietin analogue therapy) or to an active control group treated with epoetin alfa.

The study periods are as follows:

- **Screening Period:** Up to 6 weeks.
- **Treatment Period:** Subjects will be randomized (1:1) to open-label treatment with either roxadustat or epoetin alfa. Treatment duration is variable for individual subjects (estimated treatment up to 4 years). A common closeout will occur when the target number of MACE events has been accrued.
- **Post-Treatment Follow-Up Period:** 4 weeks from the end of treatment (EOT) visit to the end of study (EOS) visit. Subjects who discontinue study medication prematurely will be followed up for CV events, Hb measurements, vital status and hospitalizations until the end of the study (EOS), according to ITT principles, unless consent to participate is withdrawn.

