1.3 Number of subjects

Primary efficacy variable: With at least 600 subjects, the study will provide at least 99% power to demonstrate non-inferiority of roxadustat versus epoetin alfa for the primary efficacy endpoint (i.e., Hb change from baseline to the average level during the evaluation period defined as Week 28 until Week 52). This assumes a difference (roxadustat minus epoetin alfa) of -0.30 g/dL, a non-inferiority margin for this difference of -0.75 g/dL and a standard deviation of 1.25 g/dL.

To contribute adjudicated CV events for the pooled CV analyses across the phase 3 program: approximately 2000 subjects will be randomized in a 1:1 ratio to either roxadustat or active control, i.e. epoetin alfa. The sample size for this study is driven by the overall requirement of adjudicated CV events for the phase 3 program in dialysis-treated CKD subjects (which consists of four studies in total targeting 611 subjects with MACE events). The three other studies in the study program are FG-4592-064, 1517-CL-0613, FG-4592-063.

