4.1.1 Censoring

For analyses based on OT+7, subjects will be censored at 7 days after last intake of study drug, or the EOS visit, whichever is earliest.

For analyses based on OT+3, subjects will be censored at 3 days after last intake of study drug, or the EOS visit, whichever is earliest.

For analyses based on OT+0, subjects will be censored at last intake of study drug, or the EOS visit, whichever is earliest.

For analyses based on the ITT analysis set and FAS, subjects will be censored at their individual EOS visit, regardless of if they have discontinued study drug or not. Complete endpoint information will be pursued with every effort for all subjects, unless they exercise their right to withdraw consent. Subjects who withdraw consent will be censored at date of withdrawal of consent, and subjects who are lost to follow up (LTFU) will be censored at last available contact.

Subjects who withdraw consent and for whom only vital status (known to be alive at study closure, or date of death) may be obtained from public records, the occurrence of all components of the primary endpoint cannot be assessed, and will thus be censored at date of consent withdrawn for all analyses. However, the determination of all-cause death will utilize all publicly known mortality data, even that extending beyond date of consent withdrawal. The vital status information will be included in the analysis of all-cause death as a single endpoint, and in sensitivity analysis and tabulations. Similarly, complete information on the endpoint may not be obtained for subjects who are LTFU. Any such subject will be censored in the analysis at the last contact where all elements of the endpoint were assessed. A subject

will not be recorded as LTFU until the end of the study, after every allowable effort to get in contact has been made. Hence, it is anticipated that the number of subjects LTFU will be limited.

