5. Proportion of total time of interpolated Hb values within the interval 10-12 g/dL from week 28 until week 52 will be estimated for each subject and used as dependent variable. The difference between roxadustat and epoetin alfa will be compared using ANCOVA. Baseline Hb will be used as a covariate and the treatment groups, CV history, geographic region and dialysis duration as fixed effects. Non-inferiority between the groups will be declared, and this test as successful, if the lower bound of the 2-sided 95% confidence interval of the difference between roxadustat and epoetin alfa exceeds -0.15.
6. The average monthly IV iron use during Week 36 to EOS will be compared between the two treatment groups using a Wilcoxon Rank Sum test. Superiority will be declared if the p-value is less than 0.05.
7. Time-to-first (and proportion of subjects who received) RBC transfusion as rescue therapy, will be analysed using Cox proportional hazard model. The baseline Hb, geographic region, dialysis duration and CV history will be included as covariates. Non-inferiority will be claimed, and this test successful, if the upper bound of the 2-sided 95% CI for the hazard ratio (roxadustat/epoetin alfa) is less than or equal to 1.8.

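### Kaplan-Meier rates and curves for first RBC transfusion and composite rescue overstate the cumulative proportion of subjects with events, because deaths are in effect censored

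*SAP*

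**What the plan says.** SAP 4.2.3 sets one reporting scheme for all time-to-event variables. It has a Cox model for the hazard ratio, a count of subjects with an event, Kaplan-Meier event rates per arm at a time point left to the available follow-up, and a plot: "Kaplan-Meier estimates of the cumulative proportion of subjects with events will be estimated and plotted".

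The scheme covers three outputs on rescue:

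- **First RBC transfusion.** This is the seventh and last secondary endpoint in SAP 4.3.4: "Time-to-first (and proportion of subjects who received) RBC transfusion as rescue therapy, will be analysed using Cox proportional hazard model". The analysis set is OT+3. The criterion is an upper 95% limit for the hazard ratio of at most 1.8.
- **Its ITT repeat**, a sensitivity analysis in SAP 4.3.6.
- **Composite rescue** (transfusion or erythropoietin analogue), exploratory in SAP 4.3.5.2, also in OT+3.

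On censoring, SAP 4.1.1 says: "For analyses based on OT+3, subjects will be censored at 3 days after last intake of study drug", or at the EOS visit if that is earlier. ITT subjects are censored at their EOS visit, at withdrawal of consent, or at last contact if lost to follow-up. Neither rule says what happens to a subject who dies without a transfusion. No cumulative incidence function or other competing-risk method appears in the SAP.

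SAP 4.1 separately provides the crude number and percentage of subjects with each time-to-event outcome.

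**The concern.** Transfusion is a non-fatal event, and death rules out a later one. With no rule that treats death as a competing event, an untransfused subject who dies leaves the risk set as a censored observation. Kaplan-Meier then credits that subject with the same future transfusion risk as those still alive. The result describes a population in which nobody dies. It is not the share of subjects who have the event, which is how SAP 4.2.3 labels it and how a reader will take it.

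The setting makes this more than a formality. Treatment may last up to 4 years in dialysis patients. The protocol's rationale for version 7.0 describes incident dialysis patients as having higher mortality, and recruitment under that version was restricted to them. What is at stake is the accuracy of a per-arm descriptive figure for a secondary endpoint. No confirmatory decision depends on it.

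**Working it through.** **The plan's own figures.** The documents state no transfusion rate, death rate, or power for the transfusion endpoint, so there is no figure on this point to reproduce. The one power statement concerns hemoglobin (SAP 1.3). It reproduces: 300 per arm, distance to the margin 0.75 - 0.30 = 0.45 g/dL, SD 1.25 and two-sided 5% give power 0.993, against at least 99% stated. It has no bearing here.

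**Inputs (all assumed).** Constant hazards: transfusion *l* from {0.05, 0.08, 0.12} per year, death *m* from {0.04, 0.06, 0.08, 0.10} per year. For OT+3, other permanent stopping of study drug *d* = 0.15 per year.

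**Formulas.**

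- Kaplan-Meier with deaths censored: 1 - exp(-*l*t)
- Cumulative incidence with death competing: *l*/(*l*+*m*) × [1 - exp(-(*l*+*m*)t)]

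**Worked case, *l* = *m* = 0.08, 3 years.**

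- Kaplan-Meier: 1 - exp(-0.24) = 21.3%
- Cumulative incidence: 0.5 × [1 - exp(-0.48)] = 19.1%
- Excess: 2.3 points

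**Centre and extremes of the grid (percent; excess in points).**

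| *l*, *m* | Year | Kaplan-Meier | Cumulative incidence | Excess |
|---|---|---|---|---|
| 0.05, 0.04 | 1 | 4.88 | 4.78 | 0.10 |
| 0.05, 0.04 | 2 | 9.52 | 9.15 | 0.36 |
| 0.05, 0.04 | 3 | 13.93 | 13.15 | 0.78 |
| 0.08, 0.08 | 1 | 7.69 | 7.39 | 0.30 |
| 0.08, 0.08 | 2 | 14.79 | 13.69 | 1.09 |
| 0.08, 0.08 | 3 | 21.34 | 19.06 | 2.28 |
| 0.12, 0.10 | 1 | 11.31 | 10.77 | 0.54 |
| 0.12, 0.10 | 2 | 21.34 | 19.42 | 1.92 |
| 0.12, 0.10 | 3 | 30.23 | 26.35 | 3.88 |

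**Between arms.** With transfusion at 0.08 in both arms and death at 0.10 against 0.08, the 3-year excess is 2.79 against 2.28 points, a distortion of about 0.5 points. With *l* = 0.08, *m* = 0.12 against *l* = 0.10, *m* = 0.10, the 2-year excess is 1.60 against 1.64 points, so the arm with more deaths has the smaller absolute excess.

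**OT+3.** This set also censors at stopping of study drug. Treating both death and stopping as competing in the 0.08/0.08 case at 3 years gives 0.08/0.31 × [1 - exp(-0.93)] = 15.6% actually transfused on treatment. The three quantities are therefore:

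- 21.3% if nobody dies or stops treatment;
- 19.1% if nobody stops treatment;
- 15.6% actually transfused on treatment.

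**Cox model.** Censoring deaths is the standard way to estimate a cause-specific hazard ratio. In a simulation with a transfusion hazard of 0.10 per year, the cause-specific rate recovered was 0.1003.

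**The case against.** Several points on the other side stand.

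- **Other figures are reported.** The crude number and percentage appear alongside the Kaplan-Meier outputs and are not inflated by them, so a reader might wrongly infer that every reported transfusion proportion is too high. The crude figure is still no substitute for a proportion by a stated time, because follow-up varies. In a simulation with *l* = *m* = 0.10, discontinuation at 0.25 per year and follow-up spread over 0.5 to 4 years, it was 13.3%, against a 3-year cumulative incidence of 22.6%.
- **Direction between arms.** A reader might infer that the overstatement is always larger in the arm with more deaths. That holds at equal transfusion hazards, but the absolute ordering can reverse otherwise, as shown above. Where it does hold, the between-arm distortion is small.
- **Death as the only competing event does not fix OT+3.** It removes 2.3 of the 5.7 points (21.3 - 15.6) separating Kaplan-Meier from the proportion actually transfused on treatment. The remedy has to say what happens to drug stopping.
- **The censoring of deaths is inferred.** It follows from the rules in SAP 4.1.1 and the absence of any other, but it is not written. In OT+3 the date is nearly settled already: follow-up ends 3 days after the last dose, and SAP 4.1 caps a missing last-dose date at the date of death. The open question is mainly in ITT.
- **Size depends on the time point.** SAP 4.2.3 does not fix it. At 1 year the excess is at most about half a point on this grid.

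None of this makes the Kaplan-Meier curve an estimate of the quantity it is labelled as.

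**Conclusion.** The point holds for the Kaplan-Meier event rates and curve for first transfusion (OT+3 and the ITT repeat) and composite rescue. Read as the cumulative proportion of subjects with events, they are too high in both arms for any death rate above zero. Under the assumed constant rates, the excess is about 0.1-0.5 points at 1 year, 0.4-1.9 at 2 years and 0.8-3.9 at 3 years. It can differ between arms if mortality or transfusion rates differ, in a direction that the documents do not allow one to predict.

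The point does not reach the non-inferiority test. A reader might suspect that the comparison with 1.8 is compromised, but the Cox hazard ratio with deaths censored is a valid cause-specific ratio and does not use the Kaplan-Meier estimate. This is a worthwhile, low-cost correction to a descriptive result.

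**What to change.** 1. **SAP 4.2.3, ITT.** For the transfusion endpoint, report Aalen-Johansen cumulative incidence by arm with death as a competing event, and name it as the estimate of the proportion transfused. Apply the same estimator to the OT+3 transfusion and composite rescue outputs, subject to item 2.
2. **SAP 4.2.3, OT+3.** If the proportion actually transfused (or rescued) on treatment is wanted, treat permanent study drug discontinuation as a competing event as well. Otherwise label the curve as assuming that treatment continues.
3. **SAP 4.1.1.** State that follow-up for a subject who dies ends no later than the date of death. This matters mainly for ITT.
4. **No change** to the Cox model, the 1.8 margin or the testing order.

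The cost is a few SAP sentences, a little more analysis work and slightly lower plotted proportions. The estimator is a standard software option, and the date of death is already collected (Protocol 6.3.3).

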4.2.4 Difference in proportions analysis

For analysis of difference in proportions the approach by [Miettinen & Nurminen 1985](#) will be used and a 2-sided 95% confidence interval for the difference of two proportions (roxadustat vs epoetin alfa) will be computed, adjusting for stratification factors. The model will include the terms of baseline Hb, treatment group, cardiovascular history, geographic region and dialysis duration. The stratified statistics will be based on the standard normal statistic proposed by Gart and Nam 1990.

4.2.5 Analysis of Covariance (ANCOVA)

When using ANCOVA in analysis of change from baseline for a continuous variable, the mean value of all change from baseline values available within the pre-specified timeframe will be used as the dependent variable. Unless specified otherwise, baseline Hb will be used as a covariate and treatment group, cardiovascular history, geographic region and dialysis duration as fixed effects for all analyses. Any further details will be given case-by-case for each endpoint (see Section 4.3). The least squares mean estimates of change from baseline for each treatment group and their difference, and associated 95% CI will be provided.

4.2.6 Multiple imputation ANCOVA

For the primary efficacy analysis, a multiple imputation ANCOVA method (O’Kelly & Ratitch, 2014) will be used. It will be conducted with the following steps:

1. 200 datasets will be generated, using seed number 326154, where non-monotone missing Hb data will be imputed, meaning intermediate visits that subjects skip, but return for evaluations at subsequent visits. The data points are imputed assuming MAR, using the MCMC imputation model baseline Hb, CV history, geographic region and dialysis duration, and the available non-missing Hb for each scheduled week are used as covariates, by treatment group. The MCMC statement in the SAS PROC MI procedure with monotone option will be used. As a result, each dataset will only have a monotone missing data pattern.
2. For each dataset from step 1, the missing monotone data points will be imputed, which is when a subject misses one visit, and all subsequent visits. As a result, 200 imputed complete datasets will be generated.
 - Missing data at Week 2 will be imputed using the regression imputation model with baseline Hb and Hb from Week 2, CV history, geographic region and dialysis duration as terms in the model, by treatment group This will be performed with the SAS PROC MI procedure with the REGRESSION option in the MONOTONE statement.
 - Repeat for all other scheduled weeks sequentially. Subjects whose missing data were imputed for previous weeks will contribute to the imputation for the current week.
 - The regression imputation model includes an intercept and the slopes of the Hb from previous weeks.

3. Fit an ANCOVA model on each of the 200 datasets where the average of the imputed and observed Hb values between weeks 28 to 52 for each subject is taken as the dependent variable and baseline Hb, treatment group, CV history, geographic region and dialysis duration as covariates.
4. Combine the results of all 200 ANCOVA models using Rubin's rules (Rubin, 1987) with the SAS PROC MI ANALYZE procedure.

The least squares mean estimates of change from baseline for each treatment group and their difference, together with their associated 95% CI and p-value will be reported.

The exploratory efficacy endpoint of Hb change from baseline to the average between week 28 to the EOT visit will be conducted in the following steps:

1. 200 datasets will be generated, using seed number 326154, assuming a return-to-baseline values, with imputed values being sampled from a posterior Bayesian distribution of baseline Hb for all treatment groups combined, using a regression imputation model with stratification variables as predictor variables.
2. The imputations will be obtained using SAS PROC MI as follows. The input dataset will contain a set of temporary records to be used for imputation model estimation, where a new record is created for each subject, assigning their baseline Hb value to a variable representing mean Hb values from week 28 to EOT. This variable will be used as a dependent variable in a regression imputation model, thus estimating a distribution of baseline values. The MONOTONE REG statement will be used to estimate the imputation model, and the MNAR statement with MODEL option will be used to specify the subset of temporary records as described above from which the imputation model will be estimated. Once the imputation is complete, the temporary records will be removed prior to analyzing the imputed data, and for subjects whose mean Hb values from week 28 to EOT were imputed, a change from baseline will be calculated as the imputed value minus baseline Hb value.
3. Fit an ANCOVA model on each of the resulting 200 datasets where the mean change in Hb from baseline from weeks 28 to EOT for each patient is taken as the dependent variable and baseline Hb, treatment group, CV history, geographic region and dialysis duration as covariates.
4. Combine the results of all 200 ANCOVA models using Rubin's rules (Rubin, 1987) with the SAS PROC MIANALYZE.
5. Non-inferiority between roxadustat compared to epoetin alfa will be declared, and this test successful, if the lower bound of the 2-sided 95% confidence interval of the difference between roxadustat and epoetin alfa exceeds -0.75 g/dL.

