4.2.8.2 PMM –Baseline Carried Forward (roxadustat only and both groups)

The analysis is similar to PMM – Last Mean Carried Forward, with a different assumption in imputing the missing data. The imputation data will be generated similarly as last mean carried forward method described above but instead of using post-baseline observed data, only baseline data will be used. The similar analyses will be conducted in two scenarios.

- The baseline carried forward imputation will be performed for the roxadustat treatment group only, while for active control group, the imputation data will be generated using the last mean carried forward described above.
- The baseline carried forward imputation will be performed for both treatment groups.

Similarly, the Rubin’s method will be then used to combine the estimates and the differences between the least square mean differences between the two treatment groups from each of the ANCOVA analysis.

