4.3.5.1 Hb related exploratory endpoint analysis

- Mean change from baseline in Hb to the subjects mean level from week 28 to EOT will be analyzed using multiple imputation with ANCOVA as described in Section 4.2.6. The mean change from baseline will only be imputed for subjects with no measurements from week 28 to EOT. Non-inferiority of roxadustat compared to epoetin alfa will be declared, and this test as successful, if the lower bound of the 2-sided 95% confidence interval of the difference between roxadustat and epoetin alfa exceeds -0.75 g/dL.
- Mean change in Hb from baseline to the subjects mean level from week 28 to week 36 in subjects with baseline hsCRP greater than the Upper Limit Normal (ULN) will be analysed analogously as the primary efficacy endpoint. PPS will be used.
- Proportion of total time of interpolated Hb values ≥ 10 g/dL from week 28 until week 36 will be estimated for each subject and used as dependent variable. The difference between roxadustat and epoetin alfa will be compared using ANCOVA with treatment group, geographic region and CV history as fixed factors and baseline Hb and baseline eGFR as covariates. PPS will be used.
- Time to achieving target Hb for anemic (Hb < 10 g/dL at baseline) subjects who were ESA-naïve or near ESA-naïve (no ESA use ≤ 4 weeks prior to randomization). This will be analyzed analogously as Time to first rescue therapy (composite). Target Hb is achieved when Hb level is within 10-12 g/dL at two consecutive measurements.
- Estimation of median time (in weeks) to achieve target Hb for anemic (Hb < 10 g/dL who were ESA-naïve or near ESA-naïve (no ESA use ≤ 4 weeks prior to randomization), based on the definition of two consecutive Hb levels within 10-12 g/dl, by treatment arm.
- Proportion of ESA-naïve anemic patients achieved Hb response by Week 24 in the subset of patients who were anemic (Hb < 10 g/dL at baseline) and were ESA-naïve or near ESA-naïve (no ESA use ≤ 4 weeks prior to randomization).

Hb response (Yes/No), where Yes is defined as:

- Hb ≥ 11.0 g/dL and Hb increase from baseline by ≥ 1.0 g/dL, for subjects with baseline Hb > 8.0 g/dL; or
- Hb increase from baseline by ≥ 2.0 g/dL, for subjects with baseline Hb ≤ 8.0 g/dL

at two consecutive visits [dates] (with available data) separated at least 5 days during the first 24 weeks of treatment without having received rescue therapy

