4.3.6 Sensitivity analysis of efficacy endpoints

- The analysis of the primary efficacy endpoint for US will be repeated but will exclude Hb values 6 weeks after the use of rescue therapy. ITT analysis set will be used.
- The analyses of primary efficacy endpoint and the secondary efficacy endpoints will be repeated using the OT+7.
- The analysis of the US primary efficacy endpoint and the Hb related secondary efficacy endpoints will be repeated using the PPS.
- The secondary endpoint of RBC transfusion as rescue therapy will be repeated using the ITT analysis set.
- Change in Hb from baseline using MMRM. Mean change from baseline across all Hb values from week 28 to week 52 will be analysed using baseline Hb as a covariate and treatment group, visit, visit by treatment interaction, CV history, geographic region and dialysis duration as fixed effects. ITT analysis set will be used.

- Proportion of total time of interpolated Hb within the interval of 10-12 g/dL from week 28 to the EOT visit. The difference between roxadustat and epoetin alfa will be compared using an ANCOVA model with baseline Hb as a covariate, and CV history, geographic region and dialysis duration, as fixed effects. ITT analysis set will be used.
- Change in Hb from baseline using PMM – Last Mean Carried Forward, as specified in Section 4.2.8.1. ITT analysis set will be used.
- Change in Hb from baseline using PMM – PMM – Baseline Mean Carried Forward (ANCOVA), as specified in Section 4.2.8.2. ITT analysis set will be used.
- Change in Hb from baseline using PMM – Baseline Mean Carried Forward for roxadustat subjects, MAR assumption for epoetin alfa group (ANCOVA), as specified in Section 4.2.8.2. ITT analysis set will be used.

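### The exploratory week 28-to-EOT analysis imputes both arms from one pooled baseline Hb distribution, which pulls the estimate toward zero and favours its non-inferiority declaration

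*SAP*

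**What the plan says.** SAP 4.2.6 has two parts. The first, for the US primary endpoint (weeks 28 to 52), imputes missing Hb under MAR separately by treatment group. The second covers the exploratory endpoint, mean Hb change from baseline to week 28 through EOT, and works differently:

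- Assumption: "200 datasets will be generated, using seed number 326154, assuming a return-to-baseline values".
- Source of the imputed values: "with imputed values being sampled from a posterior Bayesian distribution of baseline Hb for all treatment groups combined".
- Predictors: "using a regression imputation model with stratification variables as predictor variables". SAP 1.2.3 lists these variables, and treatment arm is not among them.
- Decision rule, step 5: "Non-inferiority between roxadustat compared to epoetin alfa will be declared, and this test successful, if the lower bound" of the two-sided 95% interval exceeds -0.75 g/dL.

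SAP 4.3.5.1 repeats the rule and limits who is imputed: "The mean change from baseline will only be imputed for subjects with no measurements from week 28 to EOT". The analysis set is ITT.

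A related method appears among the pattern-mixture sensitivity analyses. One scenario in SAP 4.2.8.2 reads "The baseline carried forward imputation will be performed for both treatment groups", and SAP 4.3.6 lists it as "Baseline Mean Carried Forward (ANCOVA), as specified in Section 4.2.8.2".

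SAP 4.2.2 says that analyses outside the confirmatory sequence are interpreted descriptively.

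**The concern.** The null hypothesis of this test is that roxadustat is worse by at least 0.75 g/dL. Imputed values that carry no arm difference are cautious in a superiority test, because they dilute a benefit. In a non-inferiority test they dilute a deficit. The more data are missing, the easier the test is to pass, so poor follow-up is rewarded.

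Two statements are at stake. One is a non-inferiority declaration for the week 28-to-EOT endpoint that could be quoted in a study report as a finding. The other is the weight given to the both-groups baseline-carried-forward analysis as evidence that the primary result survives data missing not at random.

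**Working it through.** **Inputs.** From SAP 1.3: SD 1.25 g/dL, margin -0.75, planning difference -0.30, at least 600 subjects for the power statement, about 2000 randomized 1:1. From SAP 4.2.6: lower limit of a two-sided 95% interval, i.e. one-sided 2.5%. The fraction with no Hb from week 28 to EOT is not given; 0% to 30% is assumed.

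**The plan's own figure.** With 300 per arm, SE = 1.25 × √(2/300) = 0.102. The distance from -0.30 to the margin is 0.45, so power = Φ(0.45/0.102 − 1.96) = 99.3%. The stated power of at least 99% is reproduced.

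**Closed form for the imputed analysis.** Let m be the missing fraction, equal in both arms, and let every subject, missing or not, have a true difference of -0.75. Imputed subjects contribute 0, so the expected estimate is -0.75(1 − m). The probability of declaring non-inferiority is Φ(0.75m/SE − 1.96), with SE = 1.25 × √(2/1000) = 0.056 for 2000 subjects and 0.102 for 600.

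**Simulation.** Baseline Hb was regressed on the strata pooled over arms, with Bayesian draws; change was imputed value minus own baseline, followed by ANCOVA and Rubin's rules. There were 50 imputations and 1000 trials per setting at 2000 subjects, 2000 trials at 600. Assumptions not in the documents: baseline SD 1.0, residual SD 1.25, data missing completely at random.

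| Missing | Expected estimate | 2000: closed form | 2000: simulated | 600: closed form | 600: simulated |
|---|---|---|---|---|---|
| 0% | -0.75 | 2.5% | 2.6% | 2.5% | 3.1% |
| 5% | -0.71 | 9.9% | 11.4% | 5.6% | 4.6% |
| 10% | -0.675 | 26.8% | 25.8% | 11.0% | 10.2% |
| 20% | -0.60 | 76.5% | 78.6% | 31.2% | 30.1% |
| 30% | -0.525 | 98.1% | 99.5% | 59.7% | 62.5% |

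With 2000 subjects and the planned 200 imputations, 10% and 20% missing gave 25.7% and 81.0%. Leaving baseline Hb group out of the imputation model gave 22.5% and 73.7%. The rates also depend on how change correlates with baseline: in a separate run (20 imputations, 600 trials) they were 22% and 69% with no correlation, and 28% and 90% with a slope of -0.7.

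**Unequal missingness.** With missing fractions mR and mE and a true epoetin mean change c, the expected estimate is -0.75(1 − mR) − c(mR − mE). For mR = 20% and mE = 10% it is -0.60, -0.65, -0.70 and -0.75 at c = 0, 0.5, 1.0 and 1.5 g/dL. Simulated declaration rates were 80%, 47%, 13% and 1.8%. More roxadustat missingness with a large mean rise can therefore cancel the bias. The same formula shows that more epoetin missingness with a positive c would enlarge it.

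**Return to baseline actually true.** If missing subjects in both arms do return to baseline and the overall difference is still -0.75, the rates are 2.1%, 1.8% and 1.4% at 10%, 20% and 30% missing. There is no inflation.

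**Both-groups baseline carried forward.** The size differs because this method imputes visit by visit, conditional on each subject's own observed data, so partly observed subjects keep their values. A simulation with monotone dropout spread over visits (200 trials, so approximate) put the lower limit above -0.75 in 1.5%, 18%, 60% and 96% of trials at about 0%, 10%, 20% and 30% dropout with 2000 subjects, and in 2%, 7%, 18% and 32% with 600.

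**The case against.** The strongest objection is status. The endpoint is exploratory, no alpha is assigned to it, and SAP 4.2.2 makes its interpretation descriptive. A reader might infer from the rates above that the trial loses control of type I error. The documents do not support that: the US primary analysis imputes within arm under MAR, the EU primary analysis uses MMRM, and no step of the fixed sequence depends on this result. What remains is that SAP 4.2.6 and 4.3.5.1 still attach a formal declaration to it.

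Second, missing subjects may not carry the deficit. Protocol 3.9.3 sends those who stop study drug permanently to conventional therapy in either arm, so their difference may be nearer zero. This is a fair reason to keep return to baseline as one scenario. It does not justify a non-inferiority conclusion that presupposes it.

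Third, the missing fraction may be small. Only subjects with no Hb at all in the window are imputed, and SAP 1.2 plans continued Hb measurement after discontinuation. On the other side, Protocol 3.9.3.2 allows modified follow-up without laboratory assessments. Nothing in the documents fixes the rate, so the 20% and 30% rows are illustrations.

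Fourth, the both-groups analysis is one of several sensitivity analyses. MMRM and own-arm last mean carried forward do not pool the arms. The roxadustat-only baseline version is a partial safeguard: it is stricter than the null only if epoetin Hb rises by more than 0.75 g/dL, and no expected rise is stated. SAP 4.2.8.1 ties the pattern-mixture models to the primary efficacy variables; none is specified for week 28 to EOT.

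**Conclusion.** The point holds for an exploratory analysis and one sensitivity analysis. As specified, the week 28-to-EOT imputation biases the estimate toward no difference and makes the non-inferiority declaration easier to reach as missing data increase.

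The inflated rates require that missing subjects share the -0.75 g/dL deficit and that missingness is about equal between arms. Under those conditions the rate is roughly four times nominal at 5% missing and ten times at 10% with 2000 subjects. At 600 subjects and 5% missing the excess is modest. It would be wrong to state the inflation as unconditional.

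The both-groups baseline-carried-forward analysis shares the direction of bias but not the exact size, so passing it is weak evidence of robustness for a non-inferiority claim. The confirmatory results themselves are not called into question.

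**What to change.** In SAP 4.2.6 (week 28 to EOT), base any non-inferiority statement on one of two alternatives:

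- Subtract 0.75 g/dL from each imputed roxadustat value before computing change from baseline. Simulated declaration rates at a true -0.75 with 2000 subjects were 2.5%, 1.8% and 1.4% at 10%, 20% and 30% missing.
- Impute within treatment arm under MAR, as the US primary analysis does. The corresponding rates were 2.7%, 2.5% and 2.1%.

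Do not combine them. Under the null, within-arm MAR already carries the deficit, so a further shift would place missing roxadustat subjects at -1.50. At 20% missing the expected estimate would be 0.8 × (-0.75) + 0.2 × (-1.50) = -0.90.

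In SAP 4.2.8.2, apply the -0.75 shift to imputed roxadustat values in the both-groups analysis. With 2000 subjects and 30% dropout this gave a rate of 0.5% and a mean estimate of -0.75.

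Keep the unshifted return-to-baseline results as descriptive output, and remove the words *declared* and *successful* from their description in 4.2.6 and 4.3.5.1.

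The cost is a few sentences, one data step and a less favourable lower limit. For the week 28-to-EOT analysis the shift lowers the estimate by about 0.75m, or 0.075 g/dL at 10% missing. At the planning difference of -0.30 and 30% missing, the shifted estimate is 0.7 × (-0.30) + 0.3 × (-0.75) = -0.435, which is 0.315 from the margin. Power is Φ(0.315/0.056 − 1.96), above 99.9%, with 2000 subjects, and Φ(0.315/0.102 − 1.96), about 87%, with 600.
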